Foot orthotics, available in both customised and off-the-shelf forms, might offer a potential solution to these challenges [24,25]. With direct-to-consumer marketing, these orthotic devices are often presented as remedies capable of alleviating an array of both foot-related issues as well as pain and discomfort [26,27]. Yet, the literature on their benefits is somewhat equivocal. Many studies have an observational or non-randomised design [28], while other studies compare custom orthotics with sham or generic insoles [29–31], which may carry their own therapeutic properties, potentially diluting the observed benefits of the customised versions. To date, however, the most compelling evidence of orthotic interventions includes the effect on specific diagnoses such as plantar fasciitis [32], and Achilles tendinopathy with moderate-to-low certainty of short-term pain reductions [33]. These conditions, while common among runners [10], are often alleviated using a comprehensive treatment approach, in which the effect of the orthotics is often assessed as an adjunct part of the treatment including patient education in combination with other interventions like physical therapy and rehab exercises [33,34], and corticosteroid injections[34]. This adjunct approach might cloud the isolated effects of the insole, and it remains uncertain whether an insole alone without patient education will prove effective in a pragmatic setting, as indeed the prescription of foot orthotics is normally associated with some degree of podiatric patient education [34].

Considering the complexities in the existing literature, there is a pressing need for a simple pragmatic trial designed to assess the immediate and prospective long-term effectiveness of customised 3D-printed insoles among the general population of recreational runners. This includes individuals with or without pain and with or without specific foot-related conditions or definitive diagnoses like plantar fasciitis. By employing intention-to-treat principles in the

primary analysis, this trial ensures a realistic representation of the insoles' real-world effectiveness in a natural setting, invaluable for both healthcare providers and runners. Our subsequent secondary analyses will then delve deeper, focusing on responses from those with significant baseline pain and specific diagnoses, offering a granular understanding of the intervention's effect across different subgroups within the recreational running community.

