5. To assess pre-trial expectations and post-trial experiences regarding the therapeutic effects of the Zoles insoles and understand their influence on the efficacy of the intervention within the specific subgroup of participants with high baseline pain levels.

Methods

Trial design

The ZOLES trial is a pragmatic, outcome assessor blinded, randomised, controlled, superiority trial, with a two-group parallel design, and a 1:1 allocation ratio. Frequent recreational runners will undergo foot scanning and thereafter be randomised to either receive a customised 3D-printed insole (Zoles ApS, Esbjerg, DK-3060, Denmark), or to be in a “do-as-usual” control group. The pragmatic design and pre-planned secondary analyses are heavily inspired by the SExSI trial [39].

The trial protocol is based on the "PREPARE Trial guide" [35] and adheres to the "SPIRIT 2013 explanation and elaboration: guidance for protocols of clinical trials" [40] and SPIRIT checklist (Appendix A). The trial report will follow the “REPORT guide” [41], and thus adhere to the CONSORT guidelines for reporting parallel group randomised trials [42], using the CONSORT extension for pragmatic trials [43], as well as the updated CONSORT-Outcomes 2022 extension [44]. The TIDieR template (Appendix B) is used to describe the intervention to aid future replication [45].

The study was approved by the St Mary’s University Ethics Sub-Committee on 4 August 2023, and the trial was pre-registered at ClinicalTrials.gov on 4 September 2023 (ID: NCT06034210) [46], before the first participant was enrolled on September 16, 2023.

Study setting

Participant screening and enrolment for this study is undertaken from Faculty of Sport, Technology and Health Sciences at St Mary’s University (Twickenham, London, United Kingdom), with recruitment to the trial being carried out at local parkrun communities, primarily from Bushy Park (Richmond upon Thames, London, United Kingdom).

Eligibility criteria

Inclusion criteria

- a) Participant is ≥ 35 years old at commencement of trial.
- b) Participant can read, speak, and understand English.
- c) Participant can receive e-mails and complete online questionnaires.
- d) Participant is a frequent runner who participate in regular parkrun activities.
- e) Participant is capable of running at commencement of trial.

Exclusion criteria

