- **Running-related injuries:** The incidence rate of injuries related to running will be monitored and reported as the number of injuries for every 1000 hours of running exposure over the 10-week duration.
- **Time-loss:** The total number of days participants miss out from running due to pain, discomfort, or injury will be tracked weekly for 10 weeks, and again at the 18-week mark.
- **Weekly Mileage:** The distance participants run every week will be recorded during the 10-week trial period, and again at the 18-week mark.
- **Weekly running exposure:** The total time participants spend running every week will be obtained in hours and minutes for the 10-week trial period, and again at the 18-week mark.
- **Adherence to intervention, ADL%:** This outcome tracks how frequently participants use the Zoles insoles for everyday activities such as sitting, standing, walking, and driving over the 10 weeks, and tracked again at the 18-week mark, and at the 52-week post-market surveillance.
- **Adherence to intervention, RUN%:** The percentage of time participants wear the Zoles insoles specifically during running will be monitored over the 10 weeks, and again at the 18-week mark, and at the 52-week post-market surveillance.
- **Adverse events from using Zoles insoles:** All adverse events associated with the usage of Zoles will be reported based on their type and number. Throughout the trial, participants will be encouraged weekly to report any adverse events through the trial

hotline. Participants will be asked again at the 52-week-post-market-surveillance to capture any long-term events.

Other Outcomes

The other outcomes of interest for the pre-planned secondary subgroup analyses include:

- **Participants achieving MCID reduction in pain:** This measure looks at the percentage of participants who manage to achieve a clinically meaningful reduction in running-related pain, defined as a reduction equal to or larger than the MCID (NRS \geq 2) as described by Salaffi et al. [48] over the 10 weeks.
- **Time until MCID reduction in pain:** This outcome gauges the time in weeks it takes for participants with clinically significant pre-existing pain (NRS \geq 3 as defined by Rathleff et al. [38]) to achieve the clinically meaningful reduction in running-related pain (MCID) during the 10-week trial period.

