The trial will include prospective data collection using e-mail-distributed surveys via REDCap (Vanderbilt University, Nashville, TN, USA). Participants receive these surveys weekly for the initial 10 weeks, facilitating the collection of real-time data on their experience, pain levels, and the impact of the customised insoles for those in the intervention group. At the conclusion of this primary trial period (week 10), participants in the control group are provided with their customized insoles, marking the commencement of an additional 8-week observation period to compare intervention response between both groups (week 18). The final follow-up occurs at the 52-week mark, again via REDCap to provide insights on their long-term experiences, adverse effects, and the sustained impact of the Zoles insoles on their running-related pain and comfort.

Reminders will automatically be sent to participants at 24 hours and 48 hours after the original time of a follow-up questionnaire to participants failing to respond. Investigators will contact participants via telephone and SMS after another 24 hours if still not responding after receiving reminders to reduce the amount of missing data.

Data management

Every participant is assigned a unique identification number, ensuring their anonymity throughout the study in compliance with the General Data Protection Regulations (GDPR) under the Data Protection Act 2018.

Data collection, both at baseline and throughout the prospective stages, is facilitated via REDCap, a secure and robust online platform renowned for its data management capabilities [56]. This process is overseen from Department of Clinical Medicine at Aalborg University (DK-9220, Aalborg Øst, Denmark) by a dedicated data handler (CD), who remains blinded to group allocation. CD and FGL constitute the Data Monitoring Committee. A list of responding and non-responding participants is generated weekly, wherefrom a list of non-responding participants to contact is generated.

The Study Director (FGL) will maintain a secured key to the participants' identities, stored on a two-factor secured personal drive, ensuring the capability to identify and withdraw individual data if necessary.

All data is safeguarded within GDPR compliant two-factor and password-protected systems at St. Mary's University server, and on the REDCap online system. These measures ensure that the data remains inaccessible to unauthorized personnel, preserving confidentiality.

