In adherence to transparency and scientific scrutiny, a fully anonymised dataset at the participant level, accompanied by the corresponding statistical code, will be made available to the public, contingent upon the requirements of the journal publishing the study's findings. This disclosure ensures the replicability and verification of the research while upholding the anonymity and privacy of all participants.

The published results will omit any information that could potentially be used to identify individual participants.

Statistical methods

The primary outcome; change in running-related pain from baseline to follow-up, will be calculated using negative binomial regression. Figure 4 illustrates a hypothetical change in pain over the course of the trial, including the expected catch-up by the control group at week 18. It is important to note, however, that the between-groups analysis for difference will adjust for

values reported at baseline [49,57]. Both the Global Rating of Change (GROC) in overall daily pain and discomfort and running-related foot/footwear comfort will be calculated similarly. Injury incidence rate ratios will be estimated per 1000 hours of running exposure using Poisson regression. Mean time-loss from running will be calculated using negative binomial regression. Adherence to the intervention will be descriptively analysed and presented, and adverse event due to the Zoles insoles will be presented in type and frequency. Every analysis in the main trial report will abide by the intention to treat principle, which means including all participants in the analyses, regardless of intervention adherence-signifying that participants will be analysed based on initial randomisation. In the primary trial report, all collected outcomes will be listed, and it will also be stated that the below-mentioned 'other pre-specified outcomes' will be reported in a subsequent secondary analysis publication with a clear reference to the primary trial registration.

Possible effect modifiers include time with allocated intervention due to possible logistics issues in handing over the insoles to the intervention group, as well as any last-minute needs for sizing adjustments if a pair of insoles do not fit inside a participant's footwear. Any new injury sustained during the trial period is another potential effect modifier. No potential external effect modifiers will be factored in the intention-to-treat analyses.

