Statistical methods – secondary subgroup analysis and post-market surveillance

The subsequent secondary analysis publication will hold the label "secondary and long-term follow-up analysis from a pragmatic randomised controlled trial" in the title. The aims of this secondary subgroup analysis study are two-fold: First, it is to investigate the immediate therapeutic effect of Zoles insoles, focusing only on participants with clinically relevant baseline pain levels (11-NRS ≥ 3) [38]. Secondly, this will include our long-term post-market analysis to evaluate the long-term effects and durability of the benefits associated with the customised 3D-printed insoles one-year post-intervention.

The between-groups difference among participants with clinically baseline pain levels will be analysed similarly to the primary outcome. Subsequent regression models will, however, also be structured to comprehend the potential influence of pre-intervention expectations and post-intervention experiences, as well as adherence to the intervention on the Zoles insoles' effectiveness within this subgroup. This involves incorporating these factors as covariates in the model.

Statistical methods – analysis population and missing data

For the primary and secondary outcomes of this trial, an intention-to-treat (ITT) analysis approach will be employed [58]. This method ensures the inclusion of all randomised participants in the analysis, irrespective of their adherence to the intervention. Participants will be analysed based on their initial randomisation. As such, any deviations from the intervention or missing follow-ups will not impact the participant's initial group classification in the analysis, as recommended by the CONSORT group [42,44].

To accommodate this approach, missing outcome data will be imputed using multiple imputations by chained equations [59]. The imputation procedure will include the following variables pre-hypothesised to potentially predict missing information: a) preceding scores relevant to the outcome in question, b) age of the participant, c) sex of the participant, d) group allocation, and d) location of recruitment (specific parkrun location).

Harms

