| | Enrolment | Allocation | Primary Study Period | | | | | | | | | | | |
| TIMEPOINT (weeks) | -1 | 0 | 1 | 2 | 3 | 4 | 5 | 6 | 7 | 8 | 9 | 10 | 18 | 52 |
| ENROLMENT: | | | | | | | | | | | | | | |
| Eligibility screen | X | | | | | | | | | | | | | |
| Informed consent | X | | | | | | | | | | | | | |
| Foot scanning | X | | | | | | | | | | | | | |
| 3D printing of insoles | X | | | | | | | | | | | | | |
| Group allocation | | X | | | | | | | | | | | | |
| INTERVENTIONS: | | | | | | | | | | | | | | |
| Intervention (Zoles) | | | | | | | | | | | | | | |
| Control ("do-as-usual" until week 10) | | | | | | | | | | | | | | |
| ASSESSMENTS: | | | | | | | | | | | | | | |
| Baseline/end of study questionnaire | | X | | | | | | | | | | | | X |
| Outcome questionnaire | | | | | | | | | | | | | X | |
| 1. Running-related pain | | | X | X | X | X | X | X | X | X | X | X | X | |
| 2. GROC | | | X | X | X | X | X | X | X | X | X | X | X | |
| 3. Foot/footwear comfort | | | X | X | X | X | X | X | X | X | X | X | X | |
| 4. 5km completion time | | | X | X | X | X | X | X | X | X | X | X | X | |
| 5. Running-related injuries | | | X | X | X | X | X | X | X | X | X | X | X | |
| 6. Time-loss from running | | | X | X | X | X | X | X | X | X | X | X | X | |
| 7. Weekly milage | | | X | X | X | X | X | X | X | X | X | X | X | |
| 8. Weekly running exposure | | | X | X | X | X | X | X | X | X | X | X | X | |
| ADHERENCE: | | | | | | | | | | | | | | |
| Adherence to intervention | | | | | X | X | X | X | X | X | X | X | X | X |
| ADVERSE EVENTS: | | | | | | | | | | | | | | |
| Adverse events from using insoles | | | | | | | | | | | | | | |

Figure 4

Appendices

A

SPIRIT checklist

B

TIDieR intervention Checklist

C

Intervention leaflet 1

D

Intervention leaflet 2

E

Participant consent materials

F

Baseline questionnaire

G

Weekly follow-up questionnaire

H

WHO Trial Registration Data Set (Version 1.3.1)

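### The injury rate ratio is to come from Poisson regression with no stated allowance for non-Poisson variation; runner-level robust standard errors would be a cheap safeguard

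*Combined protocol and SAP*

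**What the plan says.** The Statistical methods section specifies the injury analysis in one sentence: "Injury incidence rate ratios will be estimated per 1000 hours of running exposure using Poisson regression". The next sentence deals with time-loss: "Mean time-loss from running will be calculated using negative binomial regression". Under Secondary outcomes, injury incidence is to be "reported as the number of injuries for every 1000 hours of running exposure over the 10-week duration".

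Three other places bear on how the counts will vary:

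- The Background describes the intended population: "This includes individuals with or without pain and with or without specific foot-related conditions or definitive diagnoses like plantar fasciitis".
- Procedures and data collection states: "Participants receive these surveys weekly for the initial 10 weeks". Figure 3 lists "5. Running-related injuries" for each of weeks 1 to 10 and again at week 18.
- The section on analysis population and missing data says that "missing outcome data will be imputed using multiple imputations by chained equations".

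The supplied text does not say how standard errors or intervals are formed for the injury rate ratio, whether a runner may contribute more than one injury, or how a runner with no running hours is handled. The weekly questionnaire (Appendix G) is listed by title only.

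**The concern.** The usual Poisson standard error assumes that the variance of a runner's injury count equals its mean. Two plausible situations break this, in opposite directions.

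- **Unequal risk.** If some runners are more injury-prone than others at the same exposure, counts vary more than Poisson and the interval is too narrow. The broad entry criteria make this plausible, although the documents describe variation in pain and foot conditions and not in injury risk itself.
- **First injuries only.** If each runner can contribute at most one injury but all running hours stay in the denominator, counts vary less than Poisson and the interval is too wide.

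At stake is whether the interval for one secondary outcome overstates or understates the evidence that insoles change injury rates. The documents do not show which direction applies.

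**Working it through.** There is no figure in the plan to reproduce: it gives no injury rate, dispersion or power for this outcome. The check asks how far the default test departs from 5% under stated assumptions.

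**Inputs from the documents.** 100 runners per group and 15% dropout (Sample size); design "with a two-group parallel design, and a 1:1 allocation ratio" (Trial design); 10 weeks of follow-up. The two-sided 5% level is borrowed from the primary outcome's sample size calculation.

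**Assumed inputs.** Running hours gamma with mean 25 and coefficient of variation 0.5. Mean injuries per runner m = 0.1, 0.2, 0.4 or 0.6. Runner-specific risk multiplier gamma with mean 1 and variance v = 0, 0.5, 1 or 2. No true effect. Total hours are 200 × 25 = 5,000, so m = 0.1 gives 200 × 0.1 = 20 injuries, or 20/5,000 = 4 per 1000 h. The other means give 40 (8 per 1000 h), 80 (16) and 120 (24).

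**Formulas.** With Y0 and Y1 the injury totals by arm, the model-based variance of the log rate ratio is 1/Y0 + 1/Y1. The runner-level sandwich variance is the sum over arms of Σ(residual²)/Y², times n/(n − 2) with n the total number of runners.

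**Simulation.** 10,000 replicates per cell, every injury counted once and independent given risk. Default type I error:

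| Injuries (per 1000 h) | v = 0 | v = 0.5 | v = 1 | v = 2 |
|---|---|---|---|---|
| about 20 (4) | 3.7% | 4.5% | 5.2% | 6.2% |
| about 40 (8) | 4.9% | 5.8% | 6.9% | 9.6% |
| about 80 (16) | 4.7% | 7.4% | 10.7% | 15.8% |
| about 120 (24) | 5.0% | 9.6% | 14.0% | 21.1% |

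If only first injuries are counted against full exposure, default type I error over the same grid is 0.8–2.9%. Robust errors give about 3–6% in all these cells. Repeat runs agreed within simulation error; at about 40 injuries with v = 2, one gave 10.5%. With 85 runners per arm and independent injuries, the ranges are 3.6–20.8% (default) and 3.7–6.2% (robust).

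**Hand check.** With unequal risk, the ratio of true to model-based variance is R = 1 + v·m·(1 + 0.5²) = 1 + 1.25·v·m, and the large-sample type I error is 2{1 − Φ(1.96/√R)}.

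- m = 0.6, v = 1: R = 1.75, √R = 1.32, error 13.8% (simulated 14.0%).
- m = 0.6, v = 2: R = 2.5, √R = 1.58, error 21.5% (simulated 21.1%).
- First injury only, with equal hours and equal risk at m = 0.6: R = e^(−0.6) = 0.549, √R = 0.741, error 0.8% (simulated 0.8%).

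**Coverage under different assumptions** (30 hours per runner, 10 injuries per 1000 h, 85 per arm), default then robust:

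- equal risk: 95.4% and 95.1%;
- v = 1: 90.8% and 94.7%;
- v = 3: 82.6% and 93.5%;
- at most one injury per runner: 98.3% and 95.6%.

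**Few injuries.** At about 10 injuries, type I error was 1.8–2.3% by default and 1.7–2.0% with robust errors.

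**Unit of clustering.** If the data rows are runner-weeks (rate ratio 0.6, v = 3, 10 per 1000 h, 85 per arm), coverage was 88.1% by default, 89.1% with robust errors that ignore the runner, and 93.9% with runner-clustered errors. The robust errors must therefore be at runner level.

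Multiple imputation was not simulated.

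**The case against.** The strongest reply is that this is an unstated detail and not an error. Statistical methods gives no interval method for any outcome, and robust errors are compatible with the sentence on injuries. That stands. A reader might infer that the plan commits to default errors; the text does not say so.

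A reader might also infer a much larger problem from the weekly surveys: a continuing injury entered week after week as if new. With re-entry probabilities of 0.2 to 0.5, default type I error ran from 9.0% to 38.9% over the grid. The documents do not support giving this weight. Secondary outcomes speaks of an incidence rate, Statistical methods refers elsewhere to new injuries, and days missed are recorded separately as time-loss. Appendix G may settle the matter but is not shown. No counting rule in the supplied text excludes re-entry, so it remains a caveat. Robust errors would not repair a rate inflated in this way.

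The negative binomial model for time-loss does not show an oversight for injuries: days lost and injury events are different kinds of count.

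Finally, the effect is small unless injuries are frequent. Apart from values close to 10% at about 40 injuries with v = 2, double digits need about 80 to 120 injuries and v of at least 1. Nothing in the documents says that the trial will see such rates.

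**Conclusion.** The point holds as a cheap improvement to one secondary analysis, at the level of something the authors could change. Poisson regression with model-based errors gives a valid interval only when variance equals the mean, and the supplied text names nothing to protect against departures. With each injury counted once and v between 0 and 2, the error ranges from negligible at 20 injuries or fewer to about four times the nominal level at 120 (21.1% against 5%). It runs the other way if only first injuries count. These sizes rest wholly on the assumed hours, rates and risk variance. The direction cannot be read from the documents, which is a reason to prefer a method that copes with both. The primary conclusion is unaffected.

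**What to change.** In Statistical methods, specify Poisson regression on one record per runner, with log running hours as offset and runner-level robust (sandwich) standard errors, computed within each imputed dataset and then pooled. Add two clarifications:

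- Each new injury counts once. Secondary outcomes does not say this at present, so it is an addition to the plan.
- Runners with zero running hours, for whom the log offset is undefined, contribute no exposure to the rate and are reported separately.

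Negative binomial regression with the same offset can serve as a sensitivity analysis.

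The cost is a few lines of text before analysis, and a wider interval where risk is unequal. At v = 1 the median standard error is 3%, 9%, 19% and 29% larger at about 20, 40, 80 and 120 injuries; at v = 2 with about 120 injuries it is 51% larger. With equal risk and independent injuries it is essentially unchanged (ratio 0.99). The Poisson model and the rate ratio are kept.

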- **Change among participants with high baseline pain:** For participants who start the trial with clinically significant pain (NRS \geq 3) [38], their specific change in pain over the 10 weeks will be captured using a numeric rating scale from 0 (No pain at all) to 10 (Worst pain imaginable) [48].
- **Pre-trial intervention expectations:** Before the trial begins, participants will indicate their expectations regarding the therapeutic effect of the Zoles insoles on running-related pain, 5-k completion time, and footwear comfort using a 5-point Likert scale.
- **Post-trial intervention experiences:** After the trial, participants will be asked about their experiences with the Zoles intervention, indicating whether it met, exceeded, or did not meet their initial expectations via a 5-point Likert scale.
- **Post-market surveillance:** One-year post-trial, all participants (from both control and intervention groups) will be surveyed to assess the long-term effects and benefits of the Zoles insoles. This survey will include the primary outcome and all key secondary outcomes, allowing for a comprehensive evaluation over a longer period.

Participant timeline

Participants are first recruited at the finish line of local parkruns on Saturday mornings during the enrolment phase (Timepoint -1). Those interested are invited to invited to the Biomechanics Laboratory of the Faculty of Sport, Technology, and Health Sciences at St Mary's University in Twickenham, London, UK, or to an in-field assessment (for the North London area). Here, they receive detailed oral and written information about the study, and if willing to proceed, sign the written informed consent form. On this day of enrolment, participants also have their feet scanned, initiating the process that customises and orders their insoles on the spot.

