The allocation phase (Timepoint 0) commences post-enrolment, where participants are sent a baseline questionnaire. The information gathered from this questionnaire is used in the balanced block randomisation procedure. Upon completion of the baseline questionnaire, participants are set up to receive weekly follow-up surveys during the primary study period (Weeks 1-10). During this period, there is weekly follow-up on primary and secondary outcomes, delivery of allocated intervention group insoles projected before week 3, and weekly monitoring of adherence and adverse effects. In a case where a pair of insoles do not fit inside a participant's footwear, a fast-track adjustment, production, and shipment procedure takes place, ensuring a minimal delay of insole delivery of approximately one week.

In the control group step allocation period (Weeks 10-18), control group participants receive their customised insoles and all participants are sent a single event follow-up questionnaire at week 18. This questionnaire covers primary and secondary outcomes, as well as adherence and adverse effects.

Finally, post-market surveillance occurs at Timepoint Week 52, a year after the study's commencement. All participants receive a follow-up questionnaire assessing their post-trial experiences with the insoles, any adverse effects experienced during the year, and the long-term effects of the Zoles insoles (Figure 3).

Sample size

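### High-pain subgroup: entering expectations, experience and adherence only as covariates cannot show whether expectation changes the insole effect, and two of the three factors arise after randomisation

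*Combined protocol and SAP*

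**What the plan says.** Objective 5 (Secondary objectives) is to assess pre-trial expectations and post-trial experiences and to "understand their influence on the efficacy of the intervention within the specific subgroup of participants with high baseline pain levels".

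The section on statistical methods for the secondary subgroup analysis starts with a plain comparison: "The between-groups difference among participants with clinically baseline pain levels will be analysed similarly to the primary outcome". That means a negative binomial model adjusted for baseline. It then adds: "Subsequent regression models will, however, also be structured to comprehend the potential influence of pre-intervention expectations and post-intervention experiences, as well as adherence", with the insoles' effectiveness in this subgroup as the target. The method is given in one sentence: "This involves incorporating these factors as covariates in the model".

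The factors are described elsewhere:

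- **Expectations** (Other Outcomes): before the trial, "participants will indicate their expectations regarding the therapeutic effect of the Zoles insoles on running-related pain, 5-k completion time, and footwear comfort".
- **Experience** (Other Outcomes): asked after the trial, "indicating whether it met, exceeded, or did not meet their initial expectations via a 5-point Likert scale". Participant timeline places it on the week-52 questionnaire: "All participants receive a follow-up questionnaire assessing their post-trial experiences with the insoles".
- **Adherence** (Secondary outcomes): two measures, ADL% and RUN%, tracked over the 10 weeks and again later. Controls do not use Zoles insoles until they are given them at week 10 (control-group description; Procedures and data collection).

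For the subgroup outcome, "their specific change in pain over the 10 weeks will be captured using a numeric rating scale". The paragraph on the further models states neither the outcome week nor which arms enter.

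**The concern.** Influence on efficacy is a question about effect modification: does the difference between arms depend on what the participant expected? A covariate without a product term gives the association of expectation with pain and imposes one common treatment ratio at every level of expectation. The coefficient can look like influence when the treatment effect is constant, and like no influence when the effect varies widely.

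The other two factors raise a different problem. Both are measured after randomisation and can be affected by allocation or by the pain outcome. Conditioning a between-group contrast on them gives up the comparison that randomisation protects.

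At stake is the answer to a numbered objective in the planned secondary publication. The main trial result is not at stake.

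**Working it through.** The documents give no figure for these models, so there is none to reproduce. The algebra below needs no trial data. The numerical examples rest on assumptions, marked as such.

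**1. Expectation, linear form.** Let y = a + dT + bE + gTE, where T is group (1:1), E is expectation measured before randomisation, b is the prognostic slope and g is the change in treatment effect per unit of E. Because T and E are independent, leaving out the product term gives:

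- both arms: coefficient of E = b + g/2
- insole arm alone: coefficient of E = b + g

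Either way one number carries two unknowns. A check with 400,000 simulated participants gave −0.30 for (b, g) = (−0.3, 0), −0.30 for (0, −0.6) and 0.00 for (+0.3, −0.6).

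**2. Expectation, planned negative binomial form.** The treatment rate ratio is 0.6, from the 40% reduction in Sample size. Assumed: control mean 4, dispersion 0.3, a 5-point expectation item scaled to SD 1. Simulated results, N = 400,000:

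| b, g (log scale, per SD) | Coefficient without product term | Rate ratio | g from interaction model |
|---|---|---|---|
| −0.15, 0 (prognosis only) | −0.148 | 0.86 | 0.000 |
| 0, −0.30 (modification only) | −0.132 | 0.88 | −0.297 |
| +0.15, −0.30 (both) | +0.021 | 1.02 | −0.304 |

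Hand check: the weight per participant is μ/(1 + 0.3μ), which is 4/2.2 = 1.818 in controls and 2.4/1.72 = 1.395 in the insole arm. The insole share is 1.395/3.213 = 0.434, and b + 0.434g gives −0.150, −0.130 and +0.020.

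The first two rows are practically the same although their meanings are opposite. The third looks like no influence, yet the treatment rate ratio runs from 0.6 × exp(0.30) = 0.81 at −1 SD to 0.6 × exp(−0.30) = 0.44 at +1 SD. In the insole arm alone, (−0.30, 0) and (0, −0.30) both give 0.74.

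**3. Experience.** The item compares what happened with initial expectations, and those include running-related pain. It is therefore partly a rating of the result being modelled. If asked at week 52, it follows the week-10 outcome, and controls have by then had insoles too. In a one-year model it is concurrent but still rates the result. No figure is claimed here.

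**4. Adherence, only if both arms enter at week 10 with controls coded 0.** The group coefficient is then the insole-arm mean, extrapolated to zero use, minus the control mean. If benefit is proportional to use, it tends to about 0 even when the insoles work. With n per arm, and adherence mean m and SD s in the insole arm, its variance is (2σ²/n) × [1 + m²/(2s²)], compared with 2σ²/n for the plain contrast. With assumed m and s:

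- m = 0.50, s = 0.30: 1 + 0.25/0.18 = 2.39, so SE × 1.5
- m = 0.85, s = 0.15: 1 + 0.7225/0.045 = 17.06, so SE × 4.1

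**5. Precision of the interaction.** Sample size gives 100 per arm and 15% dropout, leaving 85. The pain distribution expected there has median 3 and lower quartile 2, so 50% to 75% score 3 or more: 43 to 64 per arm. Using the assumptions in step 2, before baseline adjustment, the variance of the log treatment ratio is [(1/4 + 0.3) + (1/2.4 + 0.3)]/n = 1.267/n, giving SE 0.172 (n = 43) and 0.141 (n = 64). In 500 simulated trials the interaction SE per SD was 1.02 times the treatment-effect SE, hence 0.175 and 0.144. For g = −0.30, two-sided 5%, power is Φ(0.30/SE − 1.96), or about 40% and 55%.

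**The case against.** The strongest reply is that the text never says main effects only. It says the models will be structured to study influence on effectiveness, and a product term would be one way to do so. That stands: a reader might infer that the plan commits to a model without interaction, and the documents do not support this. The defect is that no interaction is specified, while the one operation stated cannot answer the question.

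A reader might also infer that the adjusted group coefficient will be presented as the subgroup's treatment effect. Nothing says so; the plain comparison comes first and the covariate models are additional.

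Adherence appears in the methods paragraph but not in objective 5, so its handling is not a failure to meet that objective. The standard-error figures need a two-arm week-10 model with zero coding and assumed adherence values, none of which is described. If only the insole arm enters, there is no group coefficient, and what remains is to name the measure and the week.

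The timing of the experience item is not fully fixed. Participant timeline supports week 52, but Other Outcomes says only that it follows the trial, and the end-of-study row in Figure 3 does not name the item. On any of these readings it is after randomisation. It also concerns more than pain, since expectations cover 5-k time and comfort as well, so it only partly rates the modelled outcome.

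Finally, the analysis is exploratory and a proper interaction test has low power. That is true and should be disclosed, but imprecision does not make the covariate coefficient an answer to a different question.

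**Conclusion.** The point holds as a gap in specification with a definite consequence. If the stated step is followed literally, the expectation part of objective 5 is answered by a coefficient that cannot separate prognosis from effect modification. This is algebraic and does not depend on the arms or week chosen; the rate ratios of 0.86, 0.88 and 1.02 only illustrate it.

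That experience and adherence are post-randomisation follows from the documents. The 1.5- to 4.1-fold standard error is conditional and illustrative.

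A reader might infer that the trial's conclusions or the subgroup estimate are compromised. They are not: the primary intention-to-treat result and the plain baseline-adjusted subgroup comparison do not use these covariates. The change should be made before the secondary analysis.

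**What to change.** In the section on statistical methods for the secondary subgroup analysis:

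1. State that the plain baseline-adjusted model is the only estimate of the subgroup treatment effect.
2. Replace the expectation covariate with an expectation-by-group interaction (both main terms retained), using the running-related-pain item among the three expectation ratings. Report it with its confidence interval and label it exploratory.
3. Do not adjust any between-group contrast for adherence or experience.
4. Analyse adherence as an association within the insole arm, naming ADL% or RUN% and the outcome week. The main report already treats adherence descriptively.
5. Report experience descriptively, and state the week at which it is asked.

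The cost is wording only; expectations are already collected before the trial. The downsides should be stated: the interaction is imprecise (about 40% to 55% power for the assumed log interaction of −0.30 per SD with 43 to 64 per arm, before baseline adjustment), the within-arm adherence analysis is also imprecise and not causal, and the experience part of objective 5 is answered only descriptively.
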